6.1.3 Device Calibration

No device calibration is necessary

6.1.4 Storage Conditions

No specific storage conditions are necessary

6.1.5 Concomitant therapy

- 1 Use of any of the prior medications described in the 5.3.2 exclusions is to be avoided.
- 2 Use of acetaminophen is acceptable
- 3 Ibuprofen or any ANSAID may be used but it's use for any reason renders that day as a non-compliant day

3.1.1 Restrictions

no restrictions

3.2 Assessments

3.2.1 Efficacy

SNEA: Device Will be provided to the patient

1. A log will be kept document that the patient wore the device that night
2. Mark if they were wet or dry that morning
3. if the alarm sounded that night
4. whether the device was on the patient in the morning
5. A log will be kept if the patient took ibuprofen or any Ansaïd that day

GoGoband®: Device Will be provided to the patient

1. A log will be kept identifying that the patient wore the device that night
2. Mark if they were wet or dry that morning
3. if the alarm sounded that night
4. whether the device was on the patient in the morning
5. A log will be kept if the patient took ibuprofen or any ansaid that day

3.2.2 Safety

Any safety events will be reported to the investigators by the parent or patient at follow up visit or via direct call to the PI on the phone number provided on the consent. Any reportable event which in this case is considered to be a skin injury due to pressure or a burn or if a choking hazard occurred due to a cable or swallowing a portion of the device are considered serious reportable events.

Events such as refusal to wear alarm due to fear of alarm, or startling patients are not considered serious events and do not warrant reporting, but this data will be recorded and reported in the final causes for exit from the study.

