3.2.1 Potential Risks

Risks associated with the alarms:

- The risk of electric shock is minimal since the whole system is a battery operated low voltage system, the only part in contact with the patient is a heart rate monitor which is an approved Photoplethysmography (PPG). PPG technology is presently ubiquitous today in most smart watches and heart rate monitors. Similarly, the risk of shock from detachment of the wired ends in the regular alarm is minimal since it is low voltage battery system.
- As the device is being installed and during usage, cord entanglement is a possibility, and mitigated by wearing a shirt over the cord.
- Choking can be a hazard if any of the associated components are placed in the mouth. The age for this study is 6 or above which would minimize this risk, additionally we do not allow for the enrollment of children with developmental or behavioral disabilities which should further minimize this risk.
- If the user chooses to attach the alarm unit using a safety pin, use of a secure pin that does not come loose easily will mitigate this risk.
- The child may become disoriented by the sound of the alarm. To mitigate this a soft rug or padding at the bedside will help prevent injury should your child roll out of bed upon awakening. Minimizing the elevation of the bed above the floor is advisable.
- There may be no benefit from either alarm therapy
- Some children may be startled by the alarm and may not wish to continue to use the device, if so, they will exit the study.
- There is a risk that internet service at the home may be inadequate for proper functioning of the GoGoband® alarm, if so, they will need to exit the study.

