3.2.2 Potential Benefits

Nocturnal enuresis is a source of depression, social isolation, and has even been linked to teenage suicide, and physical abuse of children. It is also significant financial and emotional drain on parents and families. Current enuresis alarm treatments are marginally effective requiring parents to seek specialist medical advice, which may not be readily available, and to spend large amounts of money on drug therapy and diapers. Many parents have an aversion to giving their children medications such as DDAVP or Imipramine to manage their enuresis

because of potential side effects, even though rare. A mechanism that allows for early warning of an impending urination event to the patient and parent is a boon for society and to the patients' own self-esteem and the families economic well-being. Our non-invasive, home-based, predictive alarming system will help satisfy these treatment needs by providing a superior conditional enuresis alarm therapy while keeping the child dry at a fraction of the cost of drug therapy or diapers with virtually no negative side-effect risk.

4 Study Objectives

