3.4.3.3 Safety

The likelihood of safety issues is minimal with bedwetting alarms. Any major safety events will be reported. Also patients who drop out due to excess startling or unwillingness to continue to wear the alarm will be considered failures and included as such in the data analysis.

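### Startle and fear of the alarm are to be reported only for children who leave, so startle in children who keep using the alarm is in no planned summary and is not compared by arm.

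*Combined protocol and SAP*

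**What the plan says.** Section 3.2.1 (Potential Risks) lists startle among the alarm risks and links it to stopping: "Some children may be startled by the alarm and may not wish to continue to use the device", in which case the child exits the study.

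Section 3.2.2 (Safety) gives the general reporting route: "Any safety events will be reported to the investigators by the parent or patient at follow up visit", or by telephone. It then sets a rule for two kinds of event, refusal to wear the alarm through fear and startle. It says that refusal and "startling patients are not considered serious events and do not warrant reporting", but that "this data will be recorded and reported in the final causes for exit from the study".

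Section 3.4.3.3 (Safety), the safety part of the planned analysis, has two elements. The first is "Any major safety events will be reported". The second is that "patients who drop out due to excess startling or unwillingness to continue to wear the alarm will be considered failures". Section 3.4.5 (Handling of Missing Data) likewise scores drop-outs as failures in the analysis of success, partial response and failure.

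Section 3.3.5 (On Study Visits) has staff look for safety issues at visits 2, 3 and 4. It gives no wording for the question and attaches no summary to the answers.

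**The concern.** How many children leave because of startle depends on how many are startled and on how many of those are unwilling to go on. Leaving happens after randomisation and may differ between the devices for reasons other than startle. Two arms with the same number of startle exits could therefore differ in how often children were startled, and arms with different exits could have the same startle frequency.

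If the plan is followed as written, the final report will contain a count of startle only among those who left. A reader who wants to know how often each alarm startled children will not find it. The gap cannot be fully repaired at analysis, because no fixed question is specified and complete, equal capture in the two arms is not assured.

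What is at stake is the description of tolerability in a randomised paediatric device comparison, for a harm that the protocol itself names.

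**Working it through.** **The plan's own figure.** The plan gives no figure for startle, so there is none to reproduce. The 29 in section 3.4.2 (Sample Size Considerations) concerns treatment response and has no bearing here.

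**Step 1: look for a planned summary of startle in children who continue.**

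| Section | What it covers | Startle in continuing children? |
|---|---|---|
| 3.2.1 Efficacy (nightly log items) | Wear, wet or dry, alarm sounded, device on in the morning, anti-inflammatory use | No |
| 3.2.2 Safety | Startle and fear recorded, reported among causes for exit | Possibly recorded; not summarised |
| 3.2.3 Adverse Events | Reporting to the IRB and others; emails to study personnel | No data summary |
| 3.3.5 On Study Visits | Safety check at visits 2 to 4 | Possibly captured; not summarised |
| 3.4.3.1 Primary Analyses | Crosstabs of wetting, wear, medication, response | No |
| 3.4.3.2 Secondary Objectives Analyses | Parental waking, familial enuresis | No |
| 3.4.3.3 Safety | Major events; startle drop-outs scored as failures | No |
| 3.4.3.4 Subject Characteristics | Age, sex, questionnaire score | No |
| 3.4.5 Missing Data | Drop-outs as failures; dry/wet nights kept | No |

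The alarm log form (Appendix 2) is not in the text available, so nothing is claimed about its fields beyond the items listed in 3.2.1 (Efficacy).

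**Step 2: does failure scoring fill the gap?** No. It applies only to children who leave, and it merges startle with every other kind of failure. It moves the response comparison but yields no count of startle.

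**Step 3: how precise would a by-arm table be?** Inputs: 50 per arm (section 5.3.1, Number of Participants). The affected counts are assumptions that serve only to show precision, and are taken as equal in the two arms. Method: Newcombe 95% interval. For each arm with proportion p and n children, the Wilson limits L and U are

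(p + z²/2n ± z√[p(1−p)/n + z²/4n²]) / (1 + z²/n), with z = 1.96.

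With equal counts the estimated difference is 0 and the interval is ±√[(p − L)² + (U − p)²].

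- 5 of 50: p = 0.10, L = 0.043, U = 0.214, giving ±√(0.0565² + 0.1136²) = ±0.127.
- 10 of 50: p = 0.20, L = 0.112, U = 0.330, giving ±0.157.
- 20 of 50: p = 0.40, L = 0.276, U = 0.538, giving ±0.186.

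The Synopsis states 150 participants, not the 100 of section 5.3.1. At 75 per arm, 8, 15 or 30 affected would give ±0.104, ±0.128 or ±0.153. Either way the table is descriptive.

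**The case against.** The strongest reply is that this was a deliberate choice. Startle is expected with a device meant to wake a child, the trial is described as minimal risk, and tolerability is neither an objective nor an outcome (sections 4.2, 4.3, 5.2.1 and 5.2.2). The protocol ties startle to stopping, reports those exits, and lets them count against the device through failure scoring. No planned test or conclusion depends on startle in children who continue. All of this stands, and it is why the point is minor. It does not supply the missing count.

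Four stronger readings are tempting and are not supported:

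- **A reader might infer that startle in continuing children goes unrecorded.** Section 3.2.2 (Safety) says the data will be recorded, families can report events, and visits 2 to 4 include a safety check. The gap is in planned summary and comparison, with consistent capture not assured.
- **A reader might infer that the plan leaves unsupported its own description of treatment "with virtually no negative side-effect risk".** That phrase is background rationale in section 3.2.2 (Potential Benefits). It is not a hypothesis, objective or planned conclusion, so the trial should not be faulted for not testing it.
- **A reader might extend the exit-only rule to disorientation.** Section 3.2.1 (Potential Risks) does say "The child may become disoriented by the sound of the alarm", but treats it as a fall hazard with its own mitigation. The rule in 3.2.2 (Safety) names only startle and fear-based refusal.
- **A reader might infer that the dry-night comparison is biased by this.** Nothing here changes how dry nights or response are measured or analysed.

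**Conclusion.** The point holds as a minor weakness in tolerability reporting. As written, startle and fear of the alarm reach the report only through children who leave: as causes for exit and, unlabelled, within treatment failures. Startle in children who continue has no planned summary and no comparison by arm.

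The size of the gap is unknown. The documents give neither a startle rate nor the share of startled children who stop, and it would be wrong to attach a number. The interval widths shown describe the proposed table, not the shortfall.

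The conclusion rests on the listed sections being the whole of the planned reporting. A startle item on the unseen log form would improve capture but would not by itself create a planned summary.

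**What to change.** **Collection.** At visits 2, 3 and 4, within the existing safety check, ask the same yes/no question in both arms: since the last contact, has the child been startled by the alarm or afraid of it? Record the same item when the reason for exit is taken. Include children removed for not using the device (sections 6.1.2 and 3.3.7), since fear could lie behind non-use.

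**Reporting.** In sections 3.2.2 (Safety) and 3.4.3.3 (Safety), specify one descriptive table by arm for all randomised children:

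1. number and percent with any startle or fear-of-alarm event, whether or not they left, with the difference and its 95% confidence interval;
2. the subset who left for that reason;
3. the number not asked.

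The third line is needed because a child who was never asked would otherwise look like a child without an event.

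**Unchanged.** Seriousness classification, expedited reporting and the scoring of drop-outs as failures.

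**Cost.** One question at three existing visits, which may be virtual, and one at exit; one table; a wording change in two sections. No new patients or scheduled visits. The schedule has no exit visit, so children removed between visits may need a brief contact. The tolerability figure may look less favourable for both alarms than an exits-only count. Families know which alarm they have, which is a further reason to keep the comparison descriptive.

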3.2.3 Adverse Events Definition and Reporting

The principal investigator or the Institutional Review Board (IRB) have the authority to stop or suspend the study or require modifications.

This protocol presents minimal risks to the subjects and Unanticipated Problems Involving Risks to Subjects or Others (UPIRSOs), including adverse events, are not anticipated. In the unlikely event that such events occur, Reportable Events (which are events that are serious or life-threatening and unanticipated (or anticipated but occurring with a greater frequency than expected) and possibly, probably, or definitely related) or Unanticipated Problems Involving Risks to Subjects or Others that may require a temporary or permanent interruption of study activities will be reported immediately (if possible), followed by a written report within 5 calendar days of the Principal Investigator becoming aware of the event to the IRB (using the appropriate forms from the website) and any appropriate funding and regulatory agencies. The investigator will apprise fellow investigators and study personnel of all UPIRSOs and adverse events that occur during the conduct of this research project via email as they are reviewed by the principal investigator. The protocol's research monitor(s), IRB study sponsors, funding and regulatory agencies, and regulatory and decision-making bodies will be informed of skin injuries due to worn device or choking incidents. adverse events within 5 days of the event becoming known to the principal investigator.”

“The principal investigator or the Institutional Review Board (IRB) or have the authority to stop or suspend the study or require modifications.

3.2.4 Pharmacokinetics (if applicable)

No testing will be performed

3.2.5 Biomarkers (if applicable)

3.3 Study Procedures

3.3.1 Study Schedule

Total study time is 3 months exclusive of prestudy visit which should be within 2 months of start of study.

Prestudy entry:

- all Nocturnal enuresis patients are all evaluated with physical examination and post void residual check.
- DVQ questionnaire is administered
- Inclusion and exclusion criteria evaluated
- treated with standard urotherapy previously described.

Visit 1:

- Confirm that patient has no daytime voiding symptoms identifying patient has MNE and qualifies for study
- Offer the patient treatment Choices:

2000031281

February 20, 2024

- medical treatment if so no longer candidate for study
- Alarm therapy: If Alarm therapy is chosen: randomize into SNEA or GoGoband®
- Consent to be signed
- Dispense alarm that day or have patient return within a week to have the alarm demonstrated and how to setup and to take home.
- Subject log is given along with alarm.

Visit 2:

- 1 month virtual or in person to follow progress,
- log is handed in, scanned into my chart, faxed or emailed
- new log dispensed

Visit 3:

- 2 month virtual or in person to follow progress
- log is handed in, scanned into my chart, faxed or emailed
- a new log dispensed

Visit 4:

- 3 months virtual or in person to close out study,
- log is handed in, scanned into my chart, faxed or emailed.
- Patients are informed that they can keep the alarm and continue to use it if they wish.

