5.1 General Design Description

We propose the following study in patients who have been evaluated for primary nocturnal enuresis in our Yale New Haven Clinics.

- All patients to be evaluated for nocturnal enuresis will undergo standard evaluation and initial treatment for nocturnal enuresis which includes:
 - Assessment Of Bowel Habits,
 - Fill Out A Questionnaire To Evaluate For Voiding Dysfunction
 - Treatment with routine bedwetting protocol of:
 1. Stopping drinks 1 HR before bedtime, meals at least 3 hrs before bedtime, eliminating milk and ice cream from dinner and on, making sure that bowel movements are occurring 4 times per week and treating appropriately if necessary.
 2. On return visit bedwetters and parents will be given the option of using medication , no further treatment, or alarm therapy.
 3. If patients choose alarm therapy, they will be asked if they wish to participate in the Randomized study comparing GoGoband® vs SNEA.
 4. Alarms will be provided to the patients free of cost to participants
 5. Patients in the alarm group will be treated for 3 months continuously.
 6. Patients in the SNEA group will record nightly if they wet their clothes and the report will be recorded and reviewed weekly
 7. GoGoband® patients' data will be automatically saved on the HIPPA Compliant servers and subsequently reviewed at the end of the week.

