5.3.2 Eligibility Criteria/Vulnerable Populations

In order to be eligible to participate in this study, an individual must meet all of the following criteria:

1. Provision of signed and dated informed consent form
2. Stated willingness to comply with all study procedures and availability for the duration of the study

3. Male or female, aged 6 to 21 years
4. In good general health as evidenced by medical history and diagnosed with MNE
5. Ability to and be willing to adhere to the treatment regimen.
6. Subjects to be eligible for the Trial need to have functioning WiFi at home utilizing a home network and not a cellular tethering connection.

An individual who meets any of the following criteria will be excluded from participation in this study:

1. No patient may have had treatment of MNE in the past 6 months whether with medications or alarms
2. Current use of on ADHD medications, Tricyclics, SSRI's, NRI's or any antipsychotic medications.
3. Presence of Autistic Spectrum disorder, ADHD, genetic syndrome associated with developmental or learning disabilities
4. Treatment with another investigational drug or other intervention within last 6 months
5. Any form of Diabetes Mellitus or Diabetes Insipidus
6. No patient with known Chronic renal disease with moderate to severe renal impairment (defined as a creatinine clearance below 50mL/min).
7. No patient with known hyponatremia or a history of hyponatremia.

6 Methods

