6.1.2 Device Administration and Schedule

SNEA: Device Will be provided to the patient

1. Instruction will be provided on how to set up the device and use it
2. The device will be worn consecutively for 3 months.
3. The alarm use will be terminated if they have been dry for 3 months consecutively.

GoGoband®: Device Will be provided to the patient

1. Instruction will be provided on how to set up the device and use it
2. The device will be worn consecutively for 3 months
3. The device will follow the built in algorithm in the device to decide when to begin the weaning process.
4. The weaning process will occur automatically until there no more nights in which the system will sound impending urination alarms

Non-compliant patients will be removed from the study. Alarms will not be requested back from the participants.

Reasons for noncompliance will be the following

1. Not taking medication
2. Not using device
3. Not filling in and submitting biweekly logs.

If a bedwetting alarm breaks or is nonfunctional the device will be replaced, and the study will proceed from the last active day

Method of Assignment/Randomization (if applicable)

2000031281

February 20, 2024

Randomization will be accomplished by having 100 envelopes with 50 SNEA and 50 GoGoband® choices. The envelopes will be distributed to the sites and pulled randomly at each site.

Age matching:

After 50% enrollment in any group the average age and standard deviation of the group will be calculated and an effort to adjust enrollment so groups are age matched will be made.

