3.3.2 Informed Consent

Informed consent will be obtained from all participants, including assents from appropriately aged minors.

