3.3.4 Enrollment

The person performing the initial screening and evaluation of the patient will be the person in charge of enrolling the patient

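### Visit 1 lists randomisation above the signing of consent, against the plan's own entry criterion; the order should read eligibility, consent and assent, then envelope

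*Combined protocol and SAP*

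**What the plan says.** Section 3.3.1 (Study Schedule) sets out Visit 1 as a bulleted list. It runs: confirm that the child has no daytime symptoms and qualifies; offer the treatment choices; "Alarm therapy: If Alarm therapy is chosen: randomize into SNEA or GoGoband"; "Consent to be signed"; dispense the alarm; hand over the log.

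Other sections bear on the order:

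- Section 5.3.2, inclusion criterion 1: "Provision of signed and dated informed consent form".
- Section 3.3.2: "Informed consent will be obtained from all participants, including assents from appropriately aged minors". It gives no timing.
- Section 5.1, item 3: "If patients choose alarm therapy, they will be asked if they wish to participate in the Randomized study comparing GoGoband® vs SNEA". It mentions neither a signature nor the draw.
- Method of Assignment, under 6.1.2: "Randomization will be accomplished by having 100 envelopes with 50 SNEA and 50 GoGoband® choices", and "The envelopes will be distributed to the sites and pulled randomly at each site". It does not say that the arm is withheld until consent is signed, that opened envelopes are logged, or what becomes of an envelope when a family declines.
- Section 3.4.5 counts patients who drop out of the study as failures in the success, partial or failure analysis. Section 3.4.3.3 does the same for patients who drop out because of startling or because they will not go on wearing the alarm. Neither mentions a family that never signed.

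**The concern.** A site that works down the Visit 1 list would randomise a child who does not yet meet inclusion criterion 1. That is a contradiction within the protocol, whatever happens in practice.

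The statistical consequence follows from the order. No blinding is described, and the devices are plainly different: section 6.1.1 describes the GoGoband as a calf sensor, tablet, moisture sensor and parent app. Both alarms are free (5.1) and may be kept (3.3.1). A family hoping for the newer device could draw the standard alarm and then not sign. If such families were left out, the groups compared would no longer be the groups that were randomised. If their envelopes went back into the pool, the allocation would depend on family preference.

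**Working it through.** **Order of steps.** Set side by side, the sections give this:

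| Step | Where stated | Timing relative to the draw |
|---|---|---|
| Inclusion and exclusion criteria | 3.3.1, prestudy entry | before |
| Post-void residual | 5.3, item 4; 3.3.1, prestudy entry | before, stated explicitly in 5.3 |
| Confirmation that the child qualifies | 3.3.1, first Visit 1 bullet | before |
| Invitation to take part | 5.1, item 3 | not stated |
| Signed consent | 3.3.1, Visit 1 | listed after |
| Consent and assent | 3.3.2 | not stated |

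Only the signature is out of place. The authors do state timing when they mean it, as with the residual test, but nowhere say that consent comes before the draw.

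**Inputs for the size.** From the documents: 50 envelopes per arm (6.1.2); success of 0.5 and 0.8, power 0.8, one-sided 5% (3.4.2). Assumed, because the documents give no figure: a fraction d of families drawing SNEA decline to sign; none drawing GoGoband do; decliners would have succeeded with probability q; both alarms truly succeed in 50%; decliners are left out.

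**The plan's own figure.** Its sample size reproduces with the unpooled one-sided formula: n = (0.25 + 0.16) × ((1.645 + 0.842)/0.3)² = 28.2, rounded up to 29 per group. The present point does not depend on it.

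**Selection effect.** SNEA success among signers = (0.50 − d·q)/(1 − d). For d = 0.20 and q = 0.7 this is (0.50 − 0.14)/0.80 = 0.45. The last column is the chance that a one-sided pooled z-test at 5% declares GoGoband better.

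| SNEA refusal d | SNEA signers | Decliner success q | SNEA success among signers | Shift towards GoGoband | Rejection rate |
|---|---|---|---|---|---|
| 10% | 45 | 30% | 52.2% | −2.2 points | 3.1% |
| 10% | 45 | 50% | 50.0% | 0 | 5.0% |
| 10% | 45 | 70% | 47.8% | +2.2 points | 7.7% |
| 20% | 40 | 30% | 55.0% | −5.0 points | 1.7% |
| 20% | 40 | 50% | 50.0% | 0 | 5.0% |
| 20% | 40 | 70% | 45.0% | +5.0 points | 12.0% |

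**Power.** For 0.5 against 0.8, one-sided with the pooled test, power is 94.3% at 50 per arm, 93.2% at 45 against 50, and 91.8% at 40 against 50.

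**If refusers were kept and scored as failures.** SNEA success becomes 0.50 − d·q. For d = 0.20 this is 0.50 − 0.06 = 44% or 0.50 − 0.14 = 36%, a false gap of 6 or 14 points. For d = 0.10 it is 47% or 43%, a gap of 3 or 7 points. When refusal is confined to SNEA, every one of these gaps favours GoGoband.

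**The case against.** The best reply is that the list should not be read as a strict sequence. The bullets are unnumbered. The lines on medical treatment and alarm therapy can be read as sub-items showing where each choice leads, which would leave the main steps as offering choices, signing consent and dispensing. The extracted text cannot settle the indentation. Section 5.1 suggests that families are asked first, and section 5.3.2 requires signed consent for entry. Consent pages and the Appendix 1 flowchart were not available and might show the right order. This stands as a reason for moderate confidence. It does not remove the contradiction, because the other Visit 1 items run in time order and no available text corrects this one.

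A reader might also infer that staff could judge eligibility knowing the arm, since section 3.3.4 says "The person performing the initial screening and evaluation of the patient will be the person in charge of enrolling the patient". The documents do not support that: the clinical criteria are settled before the draw, and 3.3.4 does not say who opens the envelope or takes consent.

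Finally, the size rests wholly on assumed refusal rates. It is zero if decliners resemble signers, and it is small beside the planned 30-point contrast. That is correct, and it limits the severity.

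**Conclusion.** The inconsistency between 3.3.1 and 5.3.2 is real and should be resolved. It may be no more than drafting. Read literally, it opens a route to selection after allocation that the planned crosstab could neither detect nor correct.

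Under SNEA-only refusal of 10% to 20% and decliner success of 30% or 70%, the bias is about 2 to 5 points either way, and the one-sided error rate lies between 1.7% and 12.0% instead of 5%. Loss of power is minor. All of these figures rest on the assumptions listed with the inputs.

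Two stronger readings go beyond the text. One is that decliners would certainly disappear from the comparison: the documents do not say they are excluded, only that the drop-out rule does not clearly reach them. The other is that the order favours GoGoband: the direction depends on who declines, which is unknown. This is a should-fix point, held with moderate confidence.

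**What to change.** Reorder Visit 1 in 3.3.1 so that eligibility is confirmed, consent and assent are signed, and only then is the envelope opened. Repeat that order in 3.3.2 and check that the Appendix 1 flowchart agrees.

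Add under Method of Assignment that every opened envelope is logged and none goes back into the pool. State that every child whose envelope was opened is analysed in the assigned arm, using observed outcomes where available.

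Signing first does not stop a family refusing the alarm after the draw, so the handling of refusers has to be specified too. Counting them as failures under 3.4.5 would bias against whichever arm is refused more often. Report refusals by arm, and add a sensitivity analysis that does not automatically score them as failures.

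The cost is a few sentences and a small amount of extra analysis. No extra visits, staff or patients are needed, and the sample size is unchanged.

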5.1.1 Study Date Range and Duration

Each patient will be in the study for 90 days. The study duration will be 2 years to accrue enough patients willing to participate in the study and 1 year for data analysis and publication

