3.4.3.7 Other

3.4.4 Subsets and Covariates

3.4.5 Handling of Missing Data

Patients who drop out of the study will be considered failures for purposes of the study with regards to success vs partial or failure analysis
 Dry /wet night rates will be maintained for the overall analysis of overall dry/wet ratios regardless of the patient ceases participation

4 Trial Administration

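### Randomising at Visit 1 but allowing the alarm and log to be handed over up to a week later can create randomised children who never start, and the plan has no single rule for analysing them

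*Combined protocol and SAP*

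**What the plan says.** Under Visit 1, section 3.3.1 lists these steps in order:

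- allocation: "Alarm therapy: If Alarm therapy is chosen: randomize into SNEA or GoGoband"
- consent: "Consent to be signed"
- hand-over: "Dispense alarm that day or have patient return within a week to have the alarm demonstrated"
- the log: "Subject log is given along with alarm"

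Allocation is by envelope, drawn at each site: "Randomization will be accomplished by having 100 envelopes with 50 SNEA and 50 GoGoband® choices". No section describes blinding or says when the family learns the result.

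Two sets of rules could apply to a child who is randomised but never collects an alarm. Section 3.4.5 says "Patients who drop out of the study will be considered failures for purposes of the study", with reference to the success, partial or failure classification. It separately keeps whatever nights were recorded for the overall dry/wet ratio. Sections 6.1.2 and 3.3.7 instead remove non-compliant patients from the study and list not using the device as a ground. They do not say how removed patients are analysed.

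On timing, section 5.1.1 says "Each patient will be in the study for 90 days", and section 6.1.2 says of each device "The device will be worn consecutively for 3 months". Neither defines day 1.

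**The concern.** Randomisation protects the comparison only if what happens afterwards does not depend on knowing the arm, or if everyone randomised is followed and analysed under one clear rule. Here the written procedure allows up to a week between the draw and the start of treatment. In that week the family has neither an alarm nor a means of recording nights. It is a fair inference, though not stated, that many families will know the result, because one device is a calf sensor with tablet and app and the other is an ordinary alarm.

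A family disappointed by the draw might not come back. So might a family put off by the set-up. If the two arms lose families at different rates, the cured/partial/failure comparison is shifted by something unrelated to how either alarm works. If those children are removed instead, the groups analysed are no longer the groups randomised. Consent is listed after the randomisation line. If that order is followed, a family could also learn its arm, decline to sign, and never be counted.

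**Working it through.** **1. The plan's own figure.** Section 3.4.2 uses success of 0.5 (SNEA) and 0.8 (GoGoband), one-sided 5% error, 80% power and ratio 1, and gives 29. The unpooled two-proportion formula gives

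(0.5×0.5 + 0.8×0.2) × (1.645 + 0.842)² / 0.3² = 0.41 × 6.18 / 0.09 ≈ 28.2, rounded up to 29 per group.

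The figure reproduces. It contains no allowance for children who never start. Section 5.3.1 and the envelope count give 50 per arm, which is used below (the synopsis says 150 in total).

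**2. Effect of failure scoring.** Inputs: 50 per arm; true success 50% in both arms among children who start (the plan's SNEA figure, set equal to represent no real difference); a share d of the arm never returns and is scored as failure. The documents give no value for d, so every d here is an assumption. The background section's abandonment rate of about 30% concerns alarm treatment in the literature, not failure to collect an alarm, and is not used.

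Observed success in an arm = 0.5 × (1 − d).

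The error rate is the exact binomial probability that a one-sided 5% pooled z-test favours GoGoband.

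| Non-return, SNEA vs GoGoband | Observed success, SNEA vs GoGoband | Spurious difference (GoGoband − SNEA) | One-sided error rate |
|---|---|---|---|
| 0% vs 0% | 50.0% vs 50.0% | 0 | 4.5% |
| 5% vs 5% | 47.5% vs 47.5% | 0 | 4.5% |
| 5% vs 2% | 47.5% vs 49.0% | +1.5 points | 6.1% |
| 10% vs 2% | 45.0% vs 49.0% | +4.0 points | 9.8% |
| 15% vs 2% | 42.5% vs 49.0% | +6.5 points | 15.0% |
| 2% vs 5% | 49.0% vs 47.5% | −1.5 points | 3.2% |
| 2% vs 10% | 49.0% vs 45.0% | −4.0 points | 1.8% |

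Ten per cent of an arm is 5 of 50 families.

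**3. Equal loss.** If both arms lose the same share, the error rate stays at or below about 5% (4.5% to 5.0% for losses of 5% to 20%), but power falls. With 0.5 vs 0.8 and 50 per arm, power is 94.3% with no loss, 87.3% at 10% and 78.2% at 20% (normal approximation).

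**4. Effect of removal.** If never-starters are removed, the denominators shrink and the deflation in step 2 does not occur. What remains is possible selection bias, if the families who leave differ in prognosis and leave at different rates by arm. The documents give nothing from which to size this.

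**5. Dry/wet night ratio.** Section 3.4.5 keeps recorded nights. A child who never received a log adds none, so failure scoring does not touch this outcome; the child simply drops out of the arm's total.

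**6. The clock.** If the 90 days were counted from the draw, a delayed child would spend up to 7/90 = 7.8% of them with no alarm and no log. If they are counted from dispensing, none would be lost.

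**The case against.** A reader might infer that the procedure inflates the result in favour of GoGoband. The documents do not support that. No section says that SNEA families are less likely to return, and there are reasons pointing the other way. GoGoband needs a tablet, app, sensor and home Wi-Fi, and the Potential Risks section names inadequate home internet as a reason to leave the study for that device only. The reversed rows of the table show the error rate falling below nominal.

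A reader might also take it as settled that never-starters are scored as failures. That is one of two readings. The removal rules fit a child who never used a device at least as well, and the failure rule in section 3.4.3.3 is worded for children unwilling to carry on wearing the alarm, that is, children who had started.

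The gap may affect few families. Same-day dispensing is allowed, and section 3.3.5 describes logs and alarms being given out at the enrolment visit, which suggests that this is usual. Halving the losses in the three rows with higher SNEA loss brings the error rates to 5.2%, 6.7% and 8.5%.

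Lastly, the 90-day period and the 3 months of wear do not contradict each other on the page. Day 1 is undefined, and resuming from the last active day after a device failure suggests counting by use.

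All of this stands as a limit on direction and size. It does not remove the point: the delay is a written procedure, never-starters are possible under it, and the rules for them disagree.

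**Conclusion.** The point holds as a possible bias of unknown sign and size. Section 3.3.1 permits a gap between allocation and hand-over in an unblinded trial, and the plan gives no consistent analysis rule for a child who is lost in that gap. Under failure scoring, the assumed non-return patterns move the one-sided error rate between 1.8% and 15.0%, against 4.5% with no loss. Under removal, the risk is selection bias that cannot be quantified from the documents. The effect of failure scoring is confined to the cured/partial/failure classification. The conclusion rests on two inferences, that families learn their arm at the draw and that some do not return, and on assumed rates. It is still worth acting on, because the gap can be avoided by a small change in procedure.

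**What to change.** Change section 3.3.1 so that:

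- consent is signed before the envelope is opened;
- the envelope is opened only at the appointment at which the alarm and log are handed over, which is the return visit when there is one;
- day 1, the 90 days and Visits 2 to 4 are counted from dispensing in both arms.

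Reconcile the removal rules in sections 6.1.2 and 3.3.7 with the dropout rule in section 3.4.5, and state how any child who is randomised but never starts is analysed, both for the cured/partial/failure outcome and for the dry/wet night ratio. Report the number of such children by arm.

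The cost is small. No visit is added, since the return appointment already exists. Both alarm types must be on hand at that appointment at each clinic; the documents do not describe stock, so this needs checking. A few consented families may be lost before randomisation, but without an allocation, so the comparison is not biased. The change does not address later open-label dropout: a family can still take an alarm home and not use it.
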